This study will allow us to determine if there is reduced toxicity associated with VMAT compared to SUPR with only a modest impact on resources. Our hypothesis is that VMAT will have reduced toxicity compared with SUPR for palliative patients with bone metastases. We also hypothesize that there will be no difference between the two arms in terms of pain response, due to the fact that the doses are equal. This hypothesis is driven by the radiobiologic rationale, which defines effective RT as the ability of radiation to induce tumour cell death while sparing normal cells.

The importance in determining if there is any benefit in terms of toxicity with VMAT compared with SUPR for palliative patients with bone metastases is obvious when consequences related to its adoption are considered. As previously discussed, although the planning time has been drastically reduced, there is still an expected modest increase in resources required to carry out a VMAT plan. For patients, the pre-treatment process of VMAT is more burdensome, i.e. patients have to wait longer before receiving VMAT as compared to SUPR, due to the increased plan complexity. Therefore, it is important to consider the patient experience in relation to the RT administration.

In summary, evidence that either supports or refutes the hypothesis that VMAT will have reduced toxicity compared with SUPR for patients with bone metastases will be helpful in guiding future practices. We are not aware of any other randomized control trials (completed or ongoing) that have addressed this issue, though a London Ontario study is randomizing patients receiving palliative lung RT to SUPR vs VMAT⁹. Due to the implications of VMAT on departmental resources and patient experience, better evidence from a randomized control trial is required before the widespread use of this technique can be justified.

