3.1.2. Endpoints

Primary Endpoint:

Patient Reported Quality of life related to Radiation Induced Nausea and Vomiting (RINV) as scored by the Functional Living Index – Emesis (FLIE) at day 5 post RT start.

Secondary Endpoints

Primary efficacy outcome

- Control of RINV measured by a daily patient diary (day 1-5)

Secondary Patient Reported Outcome Measures (PROMs)

- Pain flare measured by the Brief Pain Inventory (BPI)
- Diary of medication use (specifically anti-emetics)
- PRO-CTCAE T11 – L5 & Pelvis:
 - Decreased appetite
 - Nausea
 - Vomiting
 - Diarrhea
 - Radiation skin reaction
 - Pain flare
 - Fatigue
- Pain response assessed by the Brief Pain Inventory.
- Proportion of patients who receive treatment within 1 day, 2 days, 3 days, 4 days, 5 days, or more than 5 days,
- Toxicity assessed at baseline and follow-up
- Quality of Life: single item from EORTC QLQ C-15 PAL: How would you rate your overall quality of life during the past week
- Performance status: as reported by patient with PRO-ECOG
- Cost effectiveness of SUPR vs. VMAT assessed by EQ-5D-5L

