4.1. Inclusion Criteria

Subjects must meet all of the following criteria to be eligible for participation in this study:

- Age 18 or older
- Able to provide informed consent
- Clinical diagnosis of cancer with bone metastases (biopsy not required)
- Currently being managed with palliative intent RT to 1-3 RT fields for bone metastases, at least one RT field (PTV) must (at least) partly lie within T11-L5 or pelvis.
- ECOG Performance Status 0-3
- Patient has been determined to potentially benefit from 8 Gy or 20 Gy
- Radiation Oncologist is comfortable prescribing 8 Gy in 1 fraction or 20 Gy in 5 fractions RT for bone metastases
- Negative pregnancy test result for women of child-bearing potential
- The baseline assessment must be completed within required timelines, prior to randomization.
- Patients must be accessible for treatment and follow-up. Investigators must assure themselves the patients randomized on this trial will be available for complete documentation of the treatment, adverse events, and follow-up.
- For simplicity of planning, expected GTV should be less than 20 cm based on radiological or clinical evidence
- Patient must be prescribed a 5-HT3 receptor antagonist (e.g. Ondansetron) as antiemetic prophylaxis prior to RT start.
- Patient is able and willing to complete the quality of life questionnaires, and other assessments that are a part of this study, via paper or using REDCap if they provide their email address on the informed consent

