4.8 Schedule of Assessments

Assessment	Screening: Visit-1	Baseline, Enrollment, Randomization: Visit 1	Treatment: Visit 2 (Day 1)	Treatment / Follow-Up (for 8Gy/1# patients) Visit 3 (Day 5)	Follow-Up Visit 4 (W2 post last RT) +/- 3 days	Follow-Up Final Visit (W4 post last RT) +/- 3 days
Informed Consent	X					
Inclusion/Exclusion Criteria	X					
Enrollment/ Randomization		X				
*Medical History/ Comorbidities	X					
Physical Examination	X					
€Pregnancy Test	X					
Patient Diary (provided to patient)			X	X		
**Brief Pain Inventory		X	X		X	X
**Functional Living Index - Emesis		X	X	X	X	X
PROMS		X	X		X	X
Treatment Related Data			X			
***Baseline & Follow-up		X	X		X	X
EQ-5D-5L		X			X	X

*may be done within 90 days, or 3 months, prior to enrollment

**BPI, FLIE and PROMS on Day 1 does not need to be repeated if collection was done within 7 days of first treatment (day 1).

***Baseline & Follow-up form does not need to be repeated if collection was done within 2 days of first treatment (day 1). If RT starts 3 or more days after baseline collection, or anytime medication changes (if known), this form will need to be repeated

€Urinalysis or serology – per institutional guidelines.

Protocol number v12.0; 16 Apr 2024

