9.1. Statistical Methods

Patients will be analyzed in the groups to which they are assigned (intention-to-treat). All analyses will be done using t-tests between the average scores of the two arms.

RINV will be assessed via Functional Living Index – Emesis (FLIE) scores compared between the two arms at baseline and day 5 post start of RT

Health-Related Quality of Life (HRQoL) will be measured using the EQ-5D-5L and combined with survival outcomes to explore differences in Quality Adjusted Life Year (QALY) gains or losses between treatments

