11.4. Post-Trial Follow-up

There is no planned follow-up at the end of the study. Any additional care that will be provided to Subjects after they complete or discontinue the study will involve standard of care treatment for what is normally expected for their condition.

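### EQ-5D-5L is not collected during the nausea and vomiting period, and no common QALY horizon is set although the measured window is longer for VMAT

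*Combined protocol and SAP*

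**What the plan says.** Section 3.1.2 lists "Cost effectiveness of SUPR vs. VMAT assessed by EQ-5D-5L" among the secondary endpoints. On method, section 9.1 says only that EQ-5D-5L will be "combined with survival outcomes to explore differences in Quality Adjusted Life Year (QALY) gains or losses between treatments"; the Protocol Summary and sections 9.2 and 10.1.3 repeat this. None of them gives a start date, an end date, an interpolation rule or a rule for deaths.

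In the table in section 4.8, EQ-5D-5L is marked at three points: Visit 1 (baseline and randomisation), "Follow-Up Visit 4 (W2 post last RT) +/- 3 days" and "Follow-Up Final Visit (W4 post last RT) +/- 3 days". The Day 1 and Day 5 cells are blank, although FLIE is marked at both. The footnote on repeating Day 1 forms reads "BPI, FLIE and PROMS on Day 1 does not need to be repeated if collection was done within 7 days of first treatment" and does not name EQ-5D-5L.

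On timing, section 4.1 requires that "The baseline assessment must be completed within required timelines, prior to randomization". Section 2.1 says that "patients have to wait longer before receiving VMAT as compared to SUPR". Section 11.4 says "There is no planned follow-up at the end of the study".

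**The concern.** There are two separate issues.

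- **Missing readings.** The trial is built on the idea that VMAT reduces RINV, which the diary follows over days 1 to 5 (section 3.1.2) and which section 10.1.3 divides into an early phase and a delayed phase ending five days after treatment. A utility curve with points only before treatment and two weeks after it has nothing to show for that period.
- **Unequal windows.** The curve starts before randomisation and ends at a visit timed from the last fraction, so its length includes the wait for treatment. An arm that waits longer is observed for longer. If QALYs are simply added up over the observed curve, a delay that section 2.1 treats as a burden on patients becomes a gain.

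What is at stake is the cost-effectiveness result. It bears on whether VMAT justifies its extra resource use, a question to which section 2.1 gives weight.

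**Working it through.** **1. The plan's own figure.** The documents give no figure for the QALY comparison, so there is none to reproduce. The sample size of 250 comes from FLIE (section 9.2: means 36 and 28, SD 16, alpha 0.05, power 0.9, dropout 30%). Taken as two-sided with 1:1 allocation, n per arm = 2 × (1.960 + 1.282)² × 16² / 8² = 84.1, so 85 per arm and 170 in total; 170 / 0.7 = 243. The exact t-test gives 172 / 0.7 = 246. The figure is reproduced within 3%, and nothing below changes it.

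**2. Where the readings fall.** Count day 1 as the first fraction, with five fractions on consecutive days.

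| Schedule | Last fraction | Delayed RINV phase ends | First post-treatment EQ-5D-5L (window) | Last EQ-5D-5L (window) |
|---|---|---|---|---|
| 8 Gy/1 | day 1 | day 6 | day 15 (12–18) | day 29 (26–32) |
| 20 Gy/5 | day 5 | day 10 | day 19 (16–22) | day 33 (30–36) |

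Even at the early edge of the visit window, the first reading comes 12 − 6 = 6 days (or 16 − 10 = 6 days) after the delayed phase ends. This step needs no assumption about utilities or waits.

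**3. Length of the measured window.** Days from baseline to the week-4 visit = wait + (days from first to last fraction) + 28. Dose schedule is a stratification factor, so course length should balance between arms. The ±3-day visit window has no reason to differ by arm. The wait is the term expected to differ systematically.

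**4. Size of the two quantities.** The documents give no utilities and no SUPR wait. Section 2.1 hypothesises three days for VMAT planning, which is not a difference between arms. The inputs below are therefore assumptions.

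- Elapsed-time credit if QALYs run to each patient's week-4 visit, with equal utility and survival in both arms = utility × extra days / 365.25.
  - Low: 0.4 × 1 / 365.25 = 0.0011
  - Middle: 0.6 × 3 / 365.25 = 0.0049
  - High: 0.8 × 5 / 365.25 = 0.0110
- For scale, take utility 0.6 and waits of 1 and 4 days. The 8 Gy/1 totals are 0.6 × 29 / 365.25 = 0.0476 and 0.6 × 32 / 365.25 = 0.0526 (+10%). The 20 Gy/5 totals are 0.0542 and 0.0591 (+9%).
- QALY effect of the RINV reduction assumed in section 9.2 (60% to 35%) = 0.25 × decrement × days / 365.25.
  - Low: 0.25 × 0.05 × 5 / 365.25 = 0.0002
  - High: 0.25 × 0.30 × 10 / 365.25 = 0.0021

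**5. What one Day 5 reading would do.** Suppose utility drops by 0.1 for five days, a true loss of 0.5 utility-days. With 8 Gy/1 and baseline three days before treatment, straight lines from baseline to Day 5 to week 2 span 3 + 14 = 17 days and give a loss of 0.5 × 0.1 × 17 = 0.85 utility-days, about 1.7 times too large. Each further day of waiting adds 0.05, so this error also grows with the wait.

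**The case against.** The strongest reply is that the plan never says QALYs run to the week-4 visit. The unequal window is a feature of data collection, and an analyst who fixes a common horizon removes its effect. Such a horizon is available from the planned data: the nominal week-4 visit is at least 28 days after baseline for everyone, so day 28 from randomisation lies inside the curve for nearly all who complete. This stands. It makes the horizon issue an omission in the analysis text, and the bias conditional.

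Four further points also stand in part.

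- RINV is not the only route to a utility difference. Pain response, fatigue and skin reaction are also endpoints, and the later visits may capture some of that.
- Time to treatment is itself a secondary endpoint, so the wait will be recorded.
- The protocol version is dated 16 April 2024 and recruitment was planned from 1 August 2019 to 30 June 2025. By then 1,720 of 2,160 calendar days, about 80%, had passed, so a new Day 5 form would reach only later patients.
- The analysis is exploratory, and FLIE on Day 5 already tests the main hypothesis.

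None of this supplies a utility reading in the RINV period or a stated horizon.

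**Conclusion.** The gap in EQ-5D-5L collection is established from the schedule alone: the QALY and cost-effectiveness comparison has no reading in the RINV period under either dose schedule. The measured window is longer for VMAT by the difference in wait, given the protocol's own expectation, and no common horizon is specified. If QALYs were summed to each week-4 visit, VMAT would be credited with 0.001 to 0.011 QALY of elapsed time, similar to or larger than an assumed RINV effect of 0.0002 to 0.002. These sizes rest on assumed utilities, decrements and waits.

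A reader might infer three stronger things that the documents do not support.

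- **That the planned QALY analysis is biased towards VMAT.** The horizon is undefined, so this follows only under one way of computing it.
- **That the credit dwarfs the true effect.** With the middle credit of 0.0049, the ratio is about 14 for a decrement of 0.1 over 5 days, about 5 for 0.3 over 5 days and about 2.4 for 0.3 over 10 days. At the low end, 0.0011 is below 0.0021.
- **That the lack of post-study follow-up rules out a common horizon.** Day 28 from randomisation is already covered for nearly all completers.

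The change is worth making, but it concerns a secondary, exploratory analysis. The FLIE comparison and N = 250 are unaffected.

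**What to change.** 1. **Section 4.8:** add EQ-5D-5L at Visit 3 (Day 5), where FLIE is already completed. With 20 Gy/5, Day 5 is the day of the last fraction, so one reading covers the RINV period only in part.
2. **Section 9.1:** state that QALYs are computed from randomisation to one fixed time in both arms, for example 28 days, with utility zero after death, and not to each patient's week-4 visit. Interpolate to that day. Where an early week-4 visit falls short of it, carry the last value forward; with ±3 days this is at most about three days. Record vital status at that date.
3. **Interpolation:** do not rely on a straight line from Day 5 to week 2 alone. Add a sensitivity analysis that confines the dip to the RINV period, since the straight line can overstate a short loss.
4. **Reporting:** state that for patients enrolled before the change the QALY estimate does not include the RINV period, and show results separately for patients with and without the Day 5 reading.

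The cost is one short questionnaire at an existing contact, one vital-status date and a few sentences of analysis text. The downsides are slight extra patient burden and two collection schedules within one analysis. The common-horizon rule needs no new questionnaire and also applies to patients already enrolled.

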9.2. Planned Subjects Enrolled

The primary outcome is Functional Living Index – Emesis (FLIE) score compared between the two arms at day 5 post start of RT. We expect patients in the SUPR arm to have a mean FLIE score of 36, 5 days post start of RT¹⁷. We anticipate that VMAT will have a much lower RINV impact (i.e. less decline in FLIE) and for the purpose of this study will hypothesize that the FLIE will be approximately 28. The standard deviation used for sample size calculation was 16.

Sample size was calculated with these FLIE scores. With alpha Type I error set at 0.05 and power set at 0.9, with a dropout rate of 30%, we calculated a conservative sample size of 250 patients. This dropout rate of 30% is a conservative number. We will collect patient demographics and if there is an indication that bias is being introduced because of dropout, we will consult with a statistician.

Our most important secondary outcome (primary efficacy outcome) is radiation induced nausea and vomiting (RINV) which occurs in 60% of patients who receive RT to the lower spine or pelvis^{17, 18}. Using the sample size of 250 patients (see above), this study has a power of 0.8 to detect a 25% difference in RINV (from 60% to 35%) with alpha Type I error set at 0.05 and a dropout rate of 20%. As outlined in the table below, if RINV difference is lower, or higher our power will be lower and higher, respectively.

Health-Related Quality of Life (HRQoL) will be measured using the EQ-5D-5L and combined with survival outcomes to explore differences in Quality Adjusted Life Year (QALY) gains or losses between treatments¹⁹.

Approximate sample size required

RINV 60% to 50% 1600

RINV 60% to 40% 400

Protocol number v12.0; 16 Apr 2024

RINV 60% to 35%	250
RINV 60% to 30%	175
RINV 60% to 20%	90

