5.5. Subject Compliance/Deviations

Subject compliance, such as attending study visits and completing questionnaires, will be monitored via REDCap. If any visits are not completed, investigator or delegate must call and conduct follow-up over the telephone. Missed visits must be documented in the deviation log.

Deviations to eliminate immediate hazards to study subjects must be reported to the Study PI immediately upon discovery and to the REB within 7 calendar days. All other reportable deviations must be reported to the Study PI immediately, however to the REB within 15 calendar days. See section **12.1.2 Protocol Deviations** for a list of deviations.

Protocol number v12.0; 16 Apr 2024

6. Dose Modifications

N/A.

7. Assessment of Efficacy

Treatment Response Evaluation

FLIE:

Scores on all individual questions will be weighted equally, reversed if required and summed to create an overall FLIE score. Minimum score and maximum score will be 18 and 126 respectively. A low score is favorable, reflecting less nausea and vomiting.

The paper version of the FLIE is a 7-point Likert-scale. Patients' responses will be rounded to the closest point on the scale for entry in the digital database. I.e. if the response is 1.4, this will be rounded to 1. If the response is 1.5, it will be rounded to 2.

RINV:

Complete control: no increased episodes of nausea or vomiting with no increased use of anti-emetic medication from baseline

Partial control: 1-2 increased episodes of nausea or vomiting with no increased use of anti-emetic medication compared to baseline

Uncontrolled response: 3 or more increased episodes of nausea or vomiting, or increased use of anti-emetic medication from baseline

Overall control: includes complete and partial control

Pain:

Complete response: pain score of 0 at treated site with no increase in analgesic intake (stable or reducing analgesics in daily oral morphine equivalent (OMED).

Partial response: pain reduction of 2 or more at the treated site on a scale of 0 to 10 without analgesic increase, or analgesic reduction of 25% or more from baseline without an increase in pain.

Pain progression: Increase in pain score of 2 or more above baseline at the treated site with stable OMED, or an increase of 25% or more in OMED compared with baseline with the pain score stable or 1 point above baseline.

Indeterminate response: Any response that is not captured by the complete response, partial response or pain progression definitions¹⁴.

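### The Day 5 FLIE t-test uses only patients with a Day 5 score, and any correction for dropout that may differ by arm is left to a later consultation

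*Combined protocol and SAP*

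**What the plan says.** Section 9.1 states intention-to-treat, meaning analysis by assigned arm, and then: "All analyses will be done using t-tests between the average scores of the two arms". Section 9.2 defines the endpoint: "The primary outcome is Functional Living Index – Emesis (FLIE) score compared between the two arms at day 5 post start of RT". The clock therefore starts at RT, whereas Section 4.8 places randomisation at Visit 1, before treatment.

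Section 2.1 says that "patients have to wait longer before receiving VMAT as compared to SUPR, due to the increased plan complexity". It adds that VMAT planning used to take about two weeks and is hypothesised to fall to three days. The SUPR wait is not given.

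Section 9.2 allows for 30% dropout on the primary endpoint, calls that figure conservative, and uses 20% for the RINV endpoint. On bias from dropout it says only that demographics will be collected and, "if there is an indication that bias is being introduced because of dropout, we will consult with a statistician".

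Section 7 says FLIE items are "reversed if required and summed to create an overall FLIE score", with a range of 18 to 126 and low scores favourable. It gives no rule for incomplete forms.

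**The concern.** A t-test on Day 5 means, with no missing-data rule, can use only patients who have a Day 5 score. A patient who dies or deteriorates between randomisation and RT, and never starts, has no defined primary value. The period in which that can happen is longer in the VMAT arm by the protocol's own account, and the population is palliative with ECOG status 0 to 3.

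If one arm loses more patients in poor condition, its remaining patients look better than the arm as randomised. Loss concentrated in VMAT would favour the hypothesised result. A comparison of demographics cannot reliably reveal loss driven by nausea or decline. A remedy chosen once the data are in hand also leaves the primary result open to choice.

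**Working it through.** **Inputs from Section 9.2:** "We expect patients in the SUPR arm to have a mean FLIE score of 36"; for VMAT the plan "will hypothesize that the FLIE will be approximately 28"; SD 16, alpha 0.05, power 0.90, dropout 30%, total 250. Allocation is 1:1 (Section 3.2). Sidedness is not stated; two-sided is assumed.

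**The plan's own figure.** Per arm, n = 2(1.960 + 1.282)² × 16² / 8² = 84.1, so 85, or 170 evaluable. Then 170 / 0.70 = 243. The t-based version gives 86 per arm, 172 evaluable and 246 in total. The stated 250 is reproduced.

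With 30% loss, 250 × 0.70 = 175 scores remain (87.5 per arm), and power is 0.91. The inflation covers lost precision. It does nothing about bias.

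**How bias would arise.** Let d be the proportion missing in an arm and g the number of points by which missing patients score worse (higher) than observed ones. The all-randomised mean is the observed mean plus d × g. With no true effect, the observed SUPR minus VMAT difference is

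b = (d_VMAT − d_SUPR) × g.

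Its standard error is SE = 16 × √(1/n_SUPR + 1/n_VMAT), with n = 125(1 − d). The two-sided rejection rate is 1 − Φ(1.96 − b/SE) + Φ(−1.96 − b/SE).

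The documents give neither d by arm nor g. The values below are assumptions shown as a range.

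| Missing VMAT / SUPR | SE | g = 4 | g = 8 | g = 16 |
|---|---|---|---|---|
| 30% / 30% | 2.42 | b 0; 0.050 | b 0; 0.050 | b 0; 0.050 |
| 35% / 25% | 2.43 | b 0.4; 0.053 | b 0.8; 0.063 | b 1.6; 0.101 |
| 40% / 20% | 2.44 | b 0.8; 0.062 | b 1.6; 0.100 | b 3.2; 0.258 |

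Worked cell (35% / 25%, g = 16): b = 0.10 × 16 = 1.6. SE = 16 × √(1/93.75 + 1/81.25) = 2.43, so b/SE = 0.66 and the rejection rate is 0.101.

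**Equal loss with unequal selection.** If 30% are missing in each arm but only the missing VMAT patients are worse, b = 0.30 × g. The rejection rate is 0.079, 0.168 or 0.510 for g = 4, 8 or 16. This is an extreme assumption, but it shows that equal dropout rates alone do not rule out bias.

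**In the other direction.** If observed patients differ by the full 8 points and 30% are missing per arm, the missing patients would have to differ by 8 × 0.70 / 0.30 = 18.7 points the opposite way to cancel the effect. For a just-significant difference of 1.96 × 2.42 = 4.74, the figure is 11.1 points.

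**The case against.** The strongest reply is that nothing shows the bias will occur. Thirty per cent is a cautious allowance, not a forecast. If VMAT planning does take about three days, a 20-point gap in attrition from waiting alone is hard to credit. With mild selection the error rate barely moves. All of this stands, and it is why the size is given as a range.

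The protocol also has safeguards. Early-termination assessments (Section 4.3), telephone follow-up (5.5) and contact attempts (11.5) reduce loss. Reasons for discontinuation are recorded (11.3), and time to treatment is a listed endpoint (3.1.2). Analysts are blinded to arm identity (3.2), and deviations from the statistical plan must be justified (9.3). These limit missing data and later discretion, but none says how a missing Day 5 score is analysed.

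Two stronger readings are tempting:

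- **That the t-test contradicts intention-to-treat.** It does not. Section 9.1 uses the term for analysis by assigned arm, and comparing available scores by assigned arm is consistent with that. The plan is silent on missing scores, not self-contradictory.
- **That a skipped FLIE item makes a patient look better.** That would follow only if blanks were added as zero. Section 7 does not say so, and its 18 to 126 range presupposes complete forms. An incomplete form could equally be set to missing. What the documents support is that no rule exists.

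**Conclusion.** The concern holds in a limited form. The primary analysis rests on patients with a Day 5 score, the protocol supplies a plausible reason why loss could differ by arm, and no method, trigger or sensitivity analysis is fixed in advance.

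In the differential-loss scenarios, type I error runs from 0.053 to 0.258, against a nominal 0.05. It is unchanged if loss is equal and similarly selected. These figures rest on assumed missing proportions by arm, an assumed gap of 4 to 16 points, the plan's SD of 16 for observed scores, and a two-sided test. The documents fix neither the direction nor the size of any bias. The sample size of 250 is sound and need not change.

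**What to change.** In Section 9.1, replace the t-test for Day 5 FLIE with a likelihood-based repeated-measures model:

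- **First response:** the last FLIE before RT (baseline, or Day 1 where repeated, never both), with a common mean across arms. Section 4.8 lets Day 1 be skipped if a form was collected within 7 days of first treatment, so the two must not be counted as separate visits. Randomisation guarantees a common mean only for the pre-randomisation form, so repeat the model with that form alone as a check.
- **Later responses:** Day 5, Week 2 and Week 4, with arm-by-visit and dose-stratum-by-visit terms. The latter are needed because Weeks 2 and 4 count from last RT and Day 5 from RT start. The Day 5 arm difference is primary.

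Because the baseline assessment is required before randomisation, every randomised patient contributes. A patient with baseline only says little about the Day 5 difference, however, so the model does not settle how such patients count. Therefore also:

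- State in the estimand how patients who die or never start RT are treated. Report their numbers, and the time from randomisation to RT, by arm.
- Add a delta-adjusted tipping-point analysis in which delta may differ by arm.
- State that incomplete FLIE forms are not summed as they stand, but prorated or set to missing by a rule fixed before database lock.
- In Section 9.2, replace the promise of a later consultation with this plan.

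The cost is a short addition to Section 9 and modest analysis work, with no new data. The model relies on a missing-at-random assumption; the tipping-point analysis shows how far departures from it would have to go to change the conclusion.

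### Section 9.2 states power of 0.8 for RINV 60% vs 35% with 250 patients; its own inputs give about 0.93 to 0.95, and the accompanying table is unlabelled and does not fit 80% power

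*Combined protocol and SAP*

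**What the plan says.** Section 9.2 (Planned Subjects Enrolled) sets the total of 250 on the primary endpoint, the FLIE score at day 5: "Sample size was calculated with these FLIE scores". It then turns to RINV: "Our most important secondary outcome (primary efficacy outcome) is radiation induced nausea and vomiting (RINV"). Sections 3.1.2 and 10.1.3 also label RINV control as the primary efficacy outcome.

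For that outcome the section keeps the same 250 patients and says "this study has a power of 0.8 to detect a 25% difference in RINV (from 60% to 35"%). The same sentence fixes the remaining inputs as alpha 0.05 and 20% dropout. It does not say whether alpha is one- or two-sided.

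For other effect sizes it refers the reader onward: "As outlined in the table below, if RINV difference is lower, or higher our power will be lower and higher, respectively". The table is headed only "Approximate sample size required". Its rows include "RINV 60% to 50% 1600" and "RINV 60% to 40% 400", followed by 250, 175 and 90 for reductions to 35%, 30% and 20%. It names no power, alpha, sidedness, dropout or formula.

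**The concern.** The sentence supplies every input to a two-proportion power calculation except sidedness and the test, so it can be checked directly. A 25-point difference with 100 evaluable patients per arm should give power well above 0.8. The table's row for 60% to 35% is 250, the same total as in the sentence, so a reader will naturally take the whole table as an 80%-power table.

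At stake is what readers believe the trial can detect on this outcome. Read as 80% power, the table says that 60% vs 40% needs 400 patients and so lies beyond this trial. A null RINV result would also look less informative than it is. Anyone planning a later study from the table would enrol too many patients for the power they think they are buying.

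**Working it through.** **Inputs.** Total 250, rates 0.60 and 0.35, alpha 0.05 and dropout 20% (Section 9.2); 1:1 allocation (Section 3.2). Evaluable per arm: 250 × 0.80 / 2 = 100. Section 9.1 names only t-tests and no test for proportions, so several standard methods were tried.

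**Power at the stated inputs.** With d = 0.25 and mean rate 0.475, the pooled-variance formula is

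power = Φ{[d√n − z₁₋α/₂ √(2 × 0.475 × 0.525)] / √(0.60 × 0.40 + 0.35 × 0.65)}

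= Φ{[0.25 × 10 − 1.960 × 0.7062] / 0.6837} = Φ(1.632) = 0.949.

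The continuity correction replaces n by (nd − 1)² / (nd²) = 24² / 6.25 = 92.16, which gives Φ{(0.25 × 9.6 − 1.384) / 0.6837} = Φ(1.486) = 0.931.

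| Case | Uncorrected | Corrected | Fisher |
|---|---|---|---|
| 20% dropout, two-sided (100 per arm) | 0.949 | 0.931 | 0.937 |
| 20% dropout, one-sided | 0.975 | 0.965 | – |
| 30% dropout, two-sided (87.5 per arm) | 0.919 | 0.892 | 0.901 (87 per arm) |
| No dropout, two-sided (125 per arm) | 0.980 | 0.973 | 0.972 |

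With 100 per arm, two-sided, the unpooled formula gives 0.955 and the arcsine formula 0.947. The stated 0.8 is not reproduced by any of these.

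**What would give 0.8.** The required number per arm is (1.960 × 0.7062 + 0.842 × 0.6837)² / 0.25² = 61.4, or 69.2 corrected. With 250 enrolled, that means dropout of 1 − 2 × 61.4 / 250 = 51% (45% corrected). Alternatively, at 100 per arm, two-sided alpha would have to be about 0.006 (0.010 corrected). Neither appears in the plan.

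**The table.** The same formula was applied to each row: two-sided alpha 0.05, rounded up per arm, doubled, divided by 0.80 for dropout and rounded up again. For 60% to 35% at 80% power, 62 × 2 / 0.80 = 155.

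| RINV 60% to | Printed | 80% power | Printed / computed | 80% power, corrected | Printed / computed | 95% power, uncorrected |
|---|---|---|---|---|---|---|
| 50% | 1600 | 970 | 1.65 | 1020 | 1.57 | 1603 |
| 40% | 400 | 243 | 1.65 | 268 | 1.49 | 400 |
| 35% | 250 | 155 | 1.61 | 175 | 1.43 | 253 |
| 30% | 175 | 105 | 1.67 | 123 | 1.42 | 173 |
| 20% | 90 | 58 | 1.55 | 70 | 1.29 | 90 |

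Every printed row is within 1.2% of the 95%-power column. Equivalently, the printed totals at 20% dropout have two-sided uncorrected power of 0.950, 0.951, 0.949, 0.954 and 0.950. Another route comes fairly close: twice the 80%-power total with no dropout gives 1549, 388, 246, 168 and 89, within 4.1%. The 95% reading is therefore the best fit, not a documented fact.

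**What 250 patients can detect at about 80% power.** For 60% vs 40% with 100 per arm, Φ{(0.20 × 10 − 1.960 × 0.7071) / 0.6928} = Φ(0.886) = 0.81. Fisher's test gives 0.79 and the corrected formula 0.77.

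**Does the total depend on this?** No. For FLIE (36 vs 28, SD 16, power 0.9, 30% dropout), 2 × (1.960 + 1.282)² × 16² / 8² = 84.1, so 85 per arm and 170 / 0.70 = 243 enrolled, consistent with 250.

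**The case against.** The strongest reply is that the error is harmless. It concerns a secondary outcome, the total rests on FLIE, and a trial with power above 0.9 certainly has at least 0.8. Most of this is right, and it limits the point: no design feature, patient risk or enrolment figure is affected. But the plan states a power of 0.8, not a minimum of 0.8, and the figure does not follow from the inputs beside it.

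A second reply is that the table never claims 80% power, so it should not be tested against that label. This stands in part: the table's own fault is that it carries no label. The text, however, sends the reader from a sentence at power 0.8 to a table with the same total for the same difference, and nothing tells the reader that the power has changed. Calling the sizes approximate cannot cover excesses of 29 to 67%.

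A third reply is that the simplest explanation is one wrong or outdated figure, the 0.8, with the table sound at 95% power. That is the likeliest reading, but only the sponsor can confirm it. The sentence is wrong whichever explanation is true.

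**Conclusion.** The concern holds. For 60% vs 35% with 250 patients and 20% dropout, power is about 0.93 to 0.95 rather than 0.80, assuming a two-sided alpha of 0.05 and 1:1 allocation. The range covers the uncorrected pooled, continuity-corrected and Fisher calculations. At 30% dropout it is 0.89 to 0.92. One-sided testing only widens the gap. The table does not represent 80% power at 20% dropout under either formula, and the documents do not show which input behind it is wrong or missing.

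This should be corrected, but its reach is limited. The misstatement is conservative, the total of 250 is unaffected, and the harm is to interpretation of the RINV result and to any later use of the table.

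**What to change.** Restate the power for 60% vs 35% with 250 patients and 20% dropout as about 0.93 to 0.95, naming the test or formula and the sidedness of alpha.

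Give the table a heading with its power, alpha, sidedness, dropout and formula. If the sponsor confirms that it was built at 95% power, labelling it so is enough. Otherwise replace the rows with 80%-power values at two-sided alpha 0.05 and 20% dropout: 970, 243, 155, 105 and 58 uncorrected, or 1020, 268, 175, 123 and 70 corrected.

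It would also help to say that 250 patients with 20% dropout have about 80% power for 60% vs 40%, quoting the value for the chosen method (0.81 uncorrected, 0.79 Fisher, 0.77 corrected).

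The cost is protocol wording and one table. No patients are added and the total does not change.
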